#### 9.5 ALT or AST Elevations

A treatment-emergent  $ALT \geq 3 \times ULN$  and/or  $AST \geq 3 \times ULN$  is considered an AE of special interest. Any participant with this laboratory result after study intervention was taken must have repeat testing within 48 to 72 hours to confirm the abnormality. For this repeat testing, the following laboratory tests must be drawn: hematology and chemistry panels, INR, serum acetaminophen level, urine drugs of abuse screen, and blood alcohol level. An extra blood serology sample must be collected and sent to the central laboratory for further diagnostic testing at a later date if needed. In addition, the investigator will perform a complete history and examination to evaluate the participant for possible liver disease.

All AEs of special interest must be reported to Allergan within 24 hours of the time the investigator becomes aware of the event using the abnormal liver function reporting form and the AE eCRF. All new elements of history, physical examination, diagnostic testing results, and other relevant medical reports are to be reported for each AE of special interest.

**If an ALT or AST  $\geq 3 \times$  ULN is confirmed, close medical follow-up is required:** For these participants, the following laboratory tests must be performed: anti-hepatitis A IgM, hepatitis B surface antigen, anti-hepatitis B core IgM, hepatitis C antibody, hepatitis C quantitative RNA by polymerase chain reaction, anti-hepatitis E IgM, anti-hepatitis E IgG, Cytomegalovirus IgM antibody and Epstein-Barr Virus IgM antibody. The participant must be followed clinically and further medical evaluation (for other causes of acute hepatic injury) should be done per the judgment of the investigator and in conjunction with medical personnel at Allergan. In general, the chemistry panel should be repeated 1 to 2 times per week to follow the course of ALT/AST elevation.

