QTcB	QT interval corrected for heart rate using the Bazett formula $(QTcB = QT/(RR)\frac{1}{2})$
QTcF	QT interval corrected for heart rate using the Fridericia formula (QTcF = QT/(RR) $\frac{1}{3}$)
SAE	serious adverse event
SAP	statistical analysis plan
SI	Le Système International d'Unités (International System of Units)
SOC	standard of care
TBL	total bilirubin
TEAE	treatment-emergent adverse event
WHO	World Health Organization
_	

4 Introduction

This statistical analysis plan (SAP) details comprehensive, technical specifications of the statistical analyses of the efficacy and safety data outlined and/or specified in the protocol amendment #3 (dated 14 May 2020) of Study 3101-301-002. Specifications of tables, figures, and data listings are contained in a separate document.

This study is a multicenter, randomized, double-blind, placebo-controlled, parallel-group study conducted in the United States and will enroll approximately 872 participants from approximately 110 sites. Participants will be randomized to one of four treatment arms (placebo, atogepant 10 mg, atogepant 30 mg, and atogepant 60 mg) in a 1:1:1:1 ratio. Approximately 70% of randomized participants will have taken at least 1 prior migraine prevention medication with proven efficacy. Randomization will be stratified based on prior exposure (yes/no) to a migraine prevention medication with proven efficacy.

[figure not shown]

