11.1 Adverse Events

Adverse events will be coded by system organ class and preferred term using the Medical Dictionary for Regulatory Activities (MedDRA), version 22.0 or newer.

An AE will be considered as a treatment-emergent adverse event (TEAE) if the AE began or worsened (increased in severity or became serious) on or after the date of the first dose of double-blind study treatment. An AE that occurs more than 30 days after the last dose of double-blind study treatment or Visit 8 whichever comes later will not be counted as a TEAE. Per case report form instructions, a new AE record will be created for any AE that worsens; therefore, TEAEs can be identified as those AEs captured in Study 3101-301-002 with recorded onset date on or after the date of the first dose of double-blind study treatment and within 30 days after the last dose of double-blind study treatment or Visit 8 whichever comes later. An AE will be considered as a treatment-emergent SAE (TESAE) if it is a TEAE that also meets SAE criteria. TEAEs that started after the date of last dose of study treatment will be considered as newly emergent.

Only AEs captured in Study 3101-301-002 will be considered for TEAEs in this study. For participants rolling over into Study 3101-309-002 (extension study) who start the first dose on Visit 1 or beyond, AEs captured in Study 3101-309-002 will be summarized in that study although some AEs might occur within 30 days after the last dose from Study 3101-301-002.

Overall summary of AEs will be provided on a per-participant basis for categories of TEAEs, treatment-related TEAEs, deaths, TESAEs, and TEAEs leading to treatment discontinuation.

The number and percentage of participants reporting TEAEs in each treatment group will be tabulated by system organ class and preferred term, and further categorized by severity to the study treatment.

SAP 3101-301-002 AGN-241689

The number and percentage of participants reporting treatment-related TEAEs in each treatment group will be tabulated by system organ class and preferred term.

The number and percentage of participants reporting newly emergent TEAEs in each treatment group will be tabulated by system organ class and preferred term.

The number and percentage of participants who have TEAEs leading to treatment discontinuation will be summarized by system organ class, preferred term and treatment group.

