Lymphocytes, absolute cell count		$< 0.7 \times LLN$	> 1.3 × ULN
Monocytes, absolute cell count		$< 0.5 \times LLN$	> 2.0 × ULN
Neutrophils, absolute cell count		$< 0.7 \times LLN$	> 1.3 × ULN
Platelet count		$< 0.5 \times LLN$	> 1.5 × ULN
Red blood cell count		< 0.9 × LLN	> 1.1 × ULN
White blood cell count	$10^{9}/L$	< 0.9 × LLN	> 1.5 × ULN
рН	рН	< 0.9 × LLN	> 1.1 × ULN
Glucose	_		At least 1+
Protein	_		At least 1+
Specific gravity			> 1.1 × ULN
	Chloride Cholesterol, total Creatinine Creatine kinase Estimated glomerular filtration rate Glucose, nonfasting Lactate dehydrogenase (LDH) Phosphorus Potassium Protein, total Sodium Triglycerides Uric acid Basophils, absolute cell count Eosinophils, absolute cell count Hematocrit Hemoglobin Lymphocytes, absolute cell count Neutrophils, absolute cell count Platelet count Red blood cell count White blood cell count pH Glucose Protein	Chloride mmol/L Cholesterol, total mmol/L Creatinine upmol/L Creatine kinase U/L Estimated glomerular filtration rate mL/min/1.73m² Glucose, nonfasting mmol/L Lactate dehydrogenase (LDH) U/L Phosphorus mmol/L Potassium mmol/L Protein, total g/L Sodium mmol/L Triglycerides mmol/L Uric acid upmol/L Basophils, absolute cell count 10°/L Eosinophils, absolute cell count 10°/L Hematocrit Ratio Hemoglobin g/L Lymphocytes, absolute cell count 10°/L Neutrophils, absolute cell count 10°/L Neutrophils absolute cell count 10°/L Platelet count 10°/L Red blood cell count 10°/L Phyle Blood cell count 10°/L Phyle Glucose —— Protein ——	Parameter SI Unit PCS Low Chloride mmol/L < 0.9 × LLN

LLN = lower limit of normal value; ULN = upper limit of normal value; normal value provided by laboratory.

The number and percentage of participants meeting each of the following criteria for postbaseline hepatic laboratory abnormalities listed in Table 11–2 will be summarized by treatment group. The percentages will be calculated relative to the number of participants with at least 1 available postbaseline assessment. The numerator will be the total number of participants having at least 1 postbaseline value that meets the specific category during the study. A supportive listing will also be provided.

SI = Le Système International d'Unités (International System of Units).

eGFR<60 mL/min/1.73m² indicates moderate eGFR decrease or worse.

Table 11-2 Criteria for Hepatic Laboratory Abnormalities

Laboratory Parameter	Categories
	≥ 1 × ULN
	≥ 1.5 × ULN
	$\geq 2 \times ULN$
ALT	\geq 3 × ULN
	≥ 5 × ULN
	≥ 10 × ULN

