	\geq 20 × ULN
	$\geq 1 \times \text{ULN}$
	≥ 1.5 × ULN
	$\geq 2 \times ULN$
AST	\geq 3 × ULN
	≥ 5 × ULN
	≥ 10 × ULN
	≥ 20 × ULN
	≥ 1 × ULN
	≥ 1.5 × ULN
	\geq 2 × ULN
ALT or AST	≥ 3 × ULN
	≥ 5 × ULN
	≥ 10 × ULN
	\geq 20 × ULN
	$\geq 1 \times \text{ULN}$
	≥ 1.5 × ULN
	$\geq 2 \times \text{ULN}$
Bilirubin Total	\geq 3 × ULN
	\geq 5 × ULN
	$\geq 10 \times \text{ULN}$
	$\geq 20 \times \text{ULN}$
	$\geq 1 \times \text{ULN}$
	≥ 1.5 × ULN
	\geq 2 × ULN
Alkaline Phosphatase	\geq 3 × ULN
	≥ 5 × ULN
	≥ 10 × ULN
	≥ 20 × ULN
Concurrent Elevations ¹	ALT or AST \geq 3 × ULN and Bilirubin Total \geq 1.5 × ULN
	ALT or AST $>= 3 \times ULN$ and Bilirubin Total $\geq 2 \times ULN$
Potential Hy's Law ¹	ALT or AST \geq 3 × ULN and Bilirubin Total \geq 2 × ULN and ALP $<$ 2 × ULN
	•

ALT = alanine aminotransferase; AST = aspartate aminotransferase; TBL = total bilirubin; ALP = alkaline phosphatase; ULN = upper limit of normal (value provided by the laboratory).

¹ Elevations are from the same day

[figure not shown]
The number and percentage of participants with an adjudicated case (i.e., $ALT \ge 3 \times ULN$) and/or $AST \ge 3 \times ULN$) will be summarized by treatment group and by relationship of ALT or AST elevation to study medication. The percentages will be calculated relative to the number of participants with at least 1 adjudicated case. The numerator will be the number of participants with at least 1 adjudicated case in the specific category of relationship. If a participant has more than 1 adjudicated case, he or she will be counted in the most relevant category of relationship.

Participants with an adjudicated case (i.e. $ALT \ge 3 \times ULN$ or $AST \ge 3 \times ULN$) will be listed with their ALT and AST assessments, adjudication dates, relationship of ALT or AST elevation to study medication, and confounding factor(s). Additional listings will be provided for participants who meet $ALT \ge 3 \times ULN$ or $AST \ge 3 \times ULN$ and/or potential Hy's law and have one of the following categories: at least 1 abnormal liver biochemistry risk factor, at least 1 liver disease sign and symptom, at least 1 liver diagnostic test performed, consultation with a specialist for liver evaluation, liver lab tests performed, and drug screen performed, respectively. A listing of urine pregnancy test results will be provided for female participants of child-bearing potential with at least one positive result.

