11.4 Electrocardiograms

Allergan

Descriptive statistics for ECG parameters (i.e., heart rate, PR interval, QRS interval, RR interval, QT interval, and QTc interval) at baseline, postbaseline, and changes from baseline values at each postbaseline timepoint will be presented by treatment group.

ECG parameter values are considered PCS if ECG values meet either the actual value or change from baseline PCS high criteria listed in Table 11-4. The number and percentage of participants with PCS postbaseline values will be tabulated by study treatment. The percentages will be calculated relative to the number of participants with an available non-PCS baseline value and at least 1 postbaseline assessment. The numerator will be the total number of participants with an available non-PCS baseline value and at least 1 PCS postbaseline ECG value during the study. A supportive listing of participants with PCS postbaseline values will be provided. A listing of all AEs for participants with PCS ECG values will also be provided.

Table 11-4 Criteria for Potentially Clinically Significant Electrocardiograms

Parameter	Unit	Criterion
QRS interval	msec	≥ 150
PR interval	msec	≥ 250
QTc (QTcB or QTcF) interval	msec	> 500
QTc (QTcB or QTcF) interval	msec	Increase from baseline > 60

QTc = QT interval corrected for heart rate.

To evaluate ECG postbaseline values of clinical interest, the number and percentage of participants with post-treatment QTcF > 450 msec, > 480 msec, and > 500 msec will be tabulated by treatment group.

The number and percentage of participants with an increase > 30 msec but \le 60 msec, and with an increase > 60 msec in QTcF will be tabulated. Participants will be counted only once for the most severe category. A supportive listing of participants with postbaseline QTcF increases > 30 msec will be provided, including the PID number, study center, and all QTc values (including changes from baseline). A listing of all AEs for participants with postbaseline QTcF increases > 30 msec will also be provided.

A shift table from baseline to the end of double-blind treatment period in the investigator's overall interpretation of the ECG will be presented by treatment group for the following categories: normal; abnormal, not clinically significant; abnormal, clinically significant. A tabular display of participants with postbaseline clinically significant ECG abnormalities according to the investigator's overall interpretation will be provided.

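### Does the adjudicated ALT/AST table hide differences between arms because its percentages are taken among cases?

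*SAP*

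**What the plan says.** The paragraph on adjudicated cases in SAP 11.2 plans a number and a percentage of participants with an adjudicated ALT and/or AST elevation of 3 x ULN or more. These "will be summarized by treatment group and by relationship of ALT or AST elevation to study medication". It then sets the denominator, "The percentages will be calculated relative to the number of participants with at least 1 adjudicated case", and the numerator, "The numerator will be the number of participants with at least 1 adjudicated case in the specific category of relationship". A participant with several cases is counted once, in a single relationship category. Each adjudicated case is also listed with its ALT and AST values, the relationship and any confounding factors.

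Earlier in the same section, Table 11-2 covers hepatic laboratory abnormalities by treatment group, including a row for ALT or AST of 3 x ULN or more. For that table: "The percentages will be calculated relative to the number of participants with at least 1 available postbaseline assessment". The ECG table in SAP 11.4 also works among assessed participants, "relative to the number of participants with an available non-PCS baseline value and at least 1 postbaseline assessment".

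SAP 11.1 adds a table by recorded causality: "The number and percentage of participants reporting treatment-related TEAEs in each treatment group". Protocol 9.5 routes these elevations to that data source as well, since they are reported "using the abnormal liver function reporting form and the AE eCRF". SAP section 4 says of the table layouts: "Specifications of tables, figures, and data listings are contained in a separate document".

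**The concern.** Having a case is an outcome that arises after randomization. A percentage conditioned on it does not compare risk between randomized arms. If the denominator is each arm's own cases, two arms with very different numbers of related elevations can show the same percentage, or even the reverse order.

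The topic gives this weight. Protocol 1.2 reports that ALT increases were seen with telcagepant and that development was stopped for that reason. Protocol 3.2 sets up blinded adjudication precisely to judge whether an elevation was related to atogepant. Other safety tables in the SAP, including Table 11-2 in the same section, use assessed participants, so the adjudicated table looks out of line. If it were the only hepatic summary by arm, a liver signal could be obscured.

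**Working it through.** The plan gives no case counts and no percentage on this point, so there is no figure to reproduce. The check sets the tables side by side and then works through assumed counts.

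**1. What each table answers**

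| Question | Planned output | Denominator |
|---|---|---|
| How many participants in each arm reach ALT or AST of 3 x ULN or more? | SAP Table 11-2 | participants with a postbaseline assessment |
| How did the committee classify the cases? | SAP 11.2, adjudicated-case paragraph | participants with an adjudicated case |
| What was each case? | SAP 11.2, listing | none (individual records) |
| How many had AEs recorded as treatment-related? | SAP 11.1 | not stated in that sentence |

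The threshold for adjudication (protocol 3.2) is the same 3 x ULN as in the Table 11-2 row. Because each participant counts in one relationship category only, the categories divide the cases without overlap. That is the structure of a distribution among cases, and cases are its natural denominator.

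**2. Assumed counts**

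Let r be the related cases, c all cases and n the participants assessed in an arm. For illustration, n = 218 (planned arm size, SAP section 15), as if everyone were assessed.

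- Arm X: r = 1, c = 2.
- Arm Y: r = 4, c = 8.

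Share among cases, r/c: 1/2 = 50% and 4/8 = 50%.

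At risk, r/n: 1/218 = 0.46% and 4/218 = 1.83%.

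The order can also reverse. With 1 of 1 against 2 of 4, the shares are 100% and 50%, while the at-risk values are 1/218 = 0.46% and 2/218 = 0.92%.

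The arithmetic behind the worry is therefore right: a share of cases is not a rate.

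**3. What the planned outputs show for arms X and Y**

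- Table 11-2 row, c/n: 2/218 = 0.92% and 8/218 = 3.67%. The fourfold difference in incidence is visible.
- Adjudicated table, r and r/c: 1 (50%) and 4 (50%). The fourfold difference in related cases is visible in the counts.

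The figure said to be missing follows from these, since (r/c) x (c/n) = r/n:

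- X: 0.50 x 0.92% = 0.46%
- Y: 0.50 x 3.67% = 1.83%

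This holds exactly if the adjudicated cases are the same participants as in the Table 11-2 row. Otherwise the printed count r over the Table 11-2 denominator gives it directly.

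**4. Sensitivity to arm size**

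SAP 18.1 reports 910 randomized, or 910/4 = 227.5 per arm. Then 1/227.5 = 0.44% and 4/227.5 = 1.76%. With 200 assessed per arm, 1/200 = 0.50% and 4/200 = 2.00%. Under equal allocation, comparing the counts leads to the same reading as comparing the rates.

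**5. Per-arm or pooled denominator**

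The SAP does not say which is meant. Pooled over these two arms, the shares are 1/10 = 10% and 4/10 = 40%, which keeps the fourfold contrast. Table 11-2 is worded in the same way, by treatment group and then relative to a number of participants, and is naturally read per arm. The adjudicated table can be read likewise.

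**The case for a change.** The strongest case for the concern is that no output described in the SAP gives, by arm, the percentage of assessed participants with an elevation that the committee judged related. Table 11-2 is not split by relationship. The treatment-related TEAE table does not fill the gap: protocol 9.1.4 gives causality to the investigator, and SAP 17.6 sets missing causality to related. On a per-arm reading, any total row in the adjudicated table would show 100% in every arm that has a case. A reader has to combine two tables to get the rate, and a single extra column would spare that work.

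All of this is factually correct, and the SAP could have stated whether the denominator is per arm or pooled. It does not show an error, though. An uninformative total row costs nothing, because the informative one is the 3 x ULN row of Table 11-2. The other tables that use assessed participants are incidence tables, so a different denominator in a classification table is not an inconsistency. The equal percentages mislead only a reader who ignores the counts printed beside them. Whether the final layout already carries an extra column cannot be known, because the table specifications are in a separate document that was not available.

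**Conclusion.** The concern does not hold. SAP 11.2 separates incidence from attribution and gives each a suitable denominator. Followed as written, the plan shows by arm how often the 3 x ULN threshold was reached among those assessed, how many cases the committee placed in each relationship category, and the details of every case. The one percentage it does not print is a quotient of two planned numbers: 0.46% and 1.83% in the assumed example with 218 per arm, or 0.44% and 1.76% with 227.5.

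This rests on counts being printed with percentages, as SAP 11.2 states, on arms of about equal size, and on the shared 3 x ULN threshold. The case counts are assumptions chosen to make the effect as plain as possible, and they say nothing about the likely result in this trial. An additional at-risk column would be a matter of presentation in a descriptive safety table. It would correct no number or rule and would change no test, alpha allocation or decision.

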11.3 Vital Signs

Descriptive statistics for vital signs (systolic and diastolic blood pressures [sitting and standing], pulse rate [sitting and standing], respiratory rate, temperature, weight, orthostatic systolic blood pressure, orthostatic diastolic blood pressure, and orthostatic pulse rate) values at baseline, postbaseline, and changes from baseline values at each postbaseline timepoint will be presented by treatment group. Orthostatic vital sign values (orthostatic systolic and diastolic blood pressures, and orthostatic pulse rate) are defined as the corresponding standing measurement minus sitting measurement of systolic and diastolic blood pressures and pulse rate respectively.

Vital sign values will be considered PCS if they meet both the observed value criterion and the change from baseline value criterion, if both criteria are available, or meet either the observed value criterion or the change from baseline value criterion that will be detailed in Table 11–3. The number and percentage of participants who have PCS postbaseline vital sign values will be tabulated by treatment group. For criteria related with systolic blood pressure, diastolic blood pressure, pulse rate and weight, the denominator will be the number of participants who have available baseline and at least 1 postbaseline assessment. For criteria related with orthostatic measures, the denominator will be the number of participants who have available non-PCS baseline and at least 1 postbaseline assessment. The numerator will be the total number of participants with at least 1 PCS postbaseline value during the study. A supportive listing of participants with PCS postbaseline values will be provided. In addition, a tabular display

showing all AEs that occurred in participants who had PCS postbaseline vital sign values will be provided.

Table 11–3 Criteria for Potentially Clinically Significant Vital Signs

D	Flag	Criteria		
Parameter		Observed Value	Change from Baseline	
C -4-1'-111	High	≥ 180	Increase of ≥ 20	
Systolic blood pressure, mm Hg	Low	≤ 90	Decrease of ≥ 20	
Disease 11 - 11 - 1	High	≥ 105	Increase of ≥ 15	
Diastolic blood pressure, mm Hg	Low	≤ 50	Decrease of ≥ 15	
D. I	High	≥ 120	Increase of ≥ 15	
Pulse rate, bpm	Low	≤ 50	Decrease of ≥ 15	
W.J.L. L.	High		Increase of ≥ 7%	
Weight, kg	Low	_	Decrease of ≥ 7%	
Orthostatic SBP change, mm Hg	Low	≤ -20	_	
Orthostatic DBP change, mm Hg	Low	≤ -15	_	
Orthostatic Pulse rate change, bpm	High	≥ 25	_	

SBP = Systolic blood pressure, DBP = Diastolic blood pressure, bpm = beats per minute.

11.4 Electrocardiograms

Allergan

Descriptive statistics for ECG parameters (i.e., heart rate, PR interval, QRS interval, RR interval, QT interval, and QTc interval) at baseline, postbaseline, and changes from baseline values at each postbaseline timepoint will be presented by treatment group.

ECG parameter values are considered PCS if ECG values meet either the actual value or change from baseline PCS high criteria listed in Table 11-4. The number and percentage of participants with PCS postbaseline values will be tabulated by study treatment. The percentages will be calculated relative to the number of participants with an available non-PCS baseline value and at least 1 postbaseline assessment. The numerator will be the total number of participants with an available non-PCS baseline value and at least 1 PCS postbaseline ECG value during the study. A supportive listing of participants with PCS postbaseline values will be provided. A listing of all AEs for participants with PCS ECG values will also be provided.

Table 11-4 Criteria for Potentially Clinically Significant Electrocardiograms

Parameter	Unit	Criterion
QRS interval	msec	≥ 150
PR interval	msec	≥ 250
QTc (QTcB or QTcF) interval	msec	> 500
QTc (QTcB or QTcF) interval	msec	Increase from baseline > 60

QTc = QT interval corrected for heart rate.

To evaluate ECG postbaseline values of clinical interest, the number and percentage of participants with post-treatment QTcF > 450 msec, > 480 msec, and > 500 msec will be tabulated by treatment group.

The number and percentage of participants with an increase > 30 msec but \le 60 msec, and with an increase > 60 msec in QTcF will be tabulated. Participants will be counted only once for the most severe category. A supportive listing of participants with postbaseline QTcF increases > 30 msec will be provided, including the PID number, study center, and all QTc values (including changes from baseline). A listing of all AEs for participants with postbaseline QTcF increases > 30 msec will also be provided.

A shift table from baseline to the end of double-blind treatment period in the investigator's overall interpretation of the ECG will be presented by treatment group for the following categories: normal; abnormal, not clinically significant; abnormal, clinically significant. A tabular display of participants with postbaseline clinically significant ECG abnormalities according to the investigator's overall interpretation will be provided.

